 H_o = Mean difference in WAZ ≤ 0.5 to look at comparisons between multiple arms
 - iv. **Weight-for-Age Z-score of (WAZ) at 6 months of infant's age**
 H_a = Mean difference in WAZ >0.5 to look at comparisons between multiple arms
 H_o = Mean difference in WAZ ≤ 0.5 to look at comparisons between multiple arms

Data cleaning and procedures

Data cleaning process will be done by these procedures:

1. Data analyst will clean the required data for the main analyses. At this point, all investigators will be blinded to the intervention each participant has been receiving.
2. The study statisticians will review the data and complete preliminary analyses for group comparisons (without knowing the actual interventions).

Definition of key variables

- i. **Length velocity**
 Length velocity to be calculated from baseline length measurement of the infants taken within 0-6 days of life and subsequent measurement in 'cm' taken at each 4 weeks interval, until the age of 6 month, calculated as cm/month.
- ii. **Growth velocity**
 Growth velocity to be calculated from baseline weight measurement of the infants taken within 0-6 days of life and subsequent measurement in 'gram' taken at each 4 weeks interval, until the age of 6 month, calculated as gm/kg/month.
- iii. **Length-for-Age Z-score (LAZ) at 6 months of infant's age**
 Length-for-age will be calculated from age, sex, and length information from the baseline measurements within 0-6 days of birth and infant anthropometry on monthly basis until 6

months of age by using the STATA WHO packages using the WHO 2006 multi-centre growth standard. The values will be expressed as Z-score units, with two decimals.

iv. Weight-for-Length Z-score (WLZ) at 6 months of infant's age

Weight-for-length will be calculated from sex, weight and length information from the baseline measurements within 0-6 days of birth and infant anthropometry on monthly basis until 6 months of age by using the STATA WHO packages using the WHO 2006 multi-centre growth standard. The values will be expressed as Z-score units, with two decimals.

v. Weight-for-Age Z-score of (WAZ) at 6 months of infant's age

Weight-for-Age will be calculated from weight, sex and gender information from the baseline measurements within 0-6 days of birth and infant anthropometry on monthly basis until 6 months of age by using the STATA WHO packages using the WHO 2006 multi-centre growth standard. The values will be expressed as Z-score units, with two decimals.

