Analysis approach

Statistical analysis will be performed by Stata, version 15. The baseline characteristics will be assessed by arm. The primary analysis will be an intention-to-treat (ITT) analysis. We will compare the mean length velocity (cm/ month) (primary outcome), weight velocity (gm/kg/day), LAZ, WLZ, and WAZ between the two intervention arms and the control arm using ANOVA, with the model adjusted for the birth weight and age of the infants at enrollment. If an outcome is missing for the intention-to-treat infants, the means from that group will be imputed.

Safety outcomes

i. Maternal serious adverse events

The occurrence of maternal SAEs will be expressed as the proportion of women with at least one SAE during the follow-up period (from enrolment to 179th day). The proportion will be calculated by dividing the number of women with at least one recorded SAE by the total number of enrolled participants. Results will be shown both as proportions of participants with any SAE as well as tabulated by the SAE category (death, hospitalization, other). If any participant has experienced more than one type of SAE, the participant will be recorded in each category.

ii. Infant serious adverse events

The occurrence of infant SAEs will be expressed as the proportion of babies with at least one SAE during the follow-up period (from enrolment to 179th day). The proportion will be

calculated by dividing the number of babies with at least one recorded SAE by the total number of recorded newborns. Results will be shown both as proportions of participants with any SAE as well as tabulated by the SAE category (death, hospitalization, other). If any participant has experienced more than one type of SAE, the participant will be recorded in each category.

Interim analysis

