11. SAMPLE SIZE CALCULATIONS & POWER ANALYSIS

The sample size is calculated and powered to look at multiple comparisons, between arms A and B, A and C plus B and C with a hypothesized higher increase with addition of Azithromycin to infant with Afzaaish in LW. Also, adjustment for multiple comparison is needed. Thus, calculations for the sample size is estimated and are per arm sample size is provided below based on the primary outcome of length velocity in LW trial with 1-sided testing, alphas to account for multiple comparison (the lower alpha), and drop out of 14% is assumed in the trial.

Assumptions for Sample Size Calculations

Variable	Difference	Std Dev	Alpha	Drop out portion	n/arm	n/arm adj dropout	Actual Power
Length Velocity	0.12	0.5	0.025	0.14	274	319	0.801

Based on assumptions, a sample size of 319 children per arm is calculated, assuming 14% drop out rate (i.e. 10% margin for loss to follow up, and 4% infants deaths).

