Length-for-Age Z-score (LAZ) at 6 months of infant's age

H_a = Mean difference in LAZ >0.5 to look at comparisons between multiple arms

H_o = Mean difference in LAZ ≤ 0.5 to look at comparisons between multiple arms

Weight-for-Length Z-score (WLZ) at 6 months of infant's age

H_a = Mean difference in WLZ >0.5 to look at comparisons between multiple arms

H_o = Mean difference in WAZ ≤ 0.5 to look at comparisons between multiple arms

Weight-for-Age Z-score of (WAZ) at 6 months of infant's age

H_a = Mean difference in WAZ >0.5 to look at comparisons between multiple arms

H_o = Mean difference in WAZ ≤ 0.5 to look at comparisons between multiple arms

6. Sample Size

There are limited data available on the impact of BEP on length velocity over the first 6 months of life in infants. However, in one of the studies, the mothers received only perinatal supplement, and the overall increase in length (cm/month) was $\beta = 3.289$ among the LNS group and $\beta = 3.346$ among the MMN group. (1) However, the women in this trial received supplements with smaller doses/energy than the women in our study will receive, and the intervention time was also different, i.e., the perinatal period rather than the infancy period. Another study showed that the difference in length velocity (cm/month) was 0.02 between the MMN and IFA groups over the period of 0-18 months. (2) Therefore, in the absence of clear evidence on the impact of these

interventions, we hypothesized the effect size to be 0.12 cm/month. This is also based on learning through field experience; when severely malnourished lactating women (MUAC < 19.0 cm) were provided with chickpea-based ready-to-eat supplements (100 gm/day for 3 months), the difference was 0.06 cm/month at 3 months of age between these women and women who did not receive any supplements (unpublished data that was used purely for implementation and was not included in a study).

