The null hypothesis for this trial is that the mean difference in length velocity between an infant of a lactating woman receiving standard breastfeeding counseling with BEP alone (Intervention arm 1) for 6 months or in combination with a single prophylactic dose of azithromycin at 42 days of age (Intervention arm 2) and an infant of a lactating woman receiving standard breastfeeding counseling alone (control arm) is equal or less than 0.12 cm/month (primary outcome). Due to the absence of evidence of such interventions on length velocity, we based this hypothesis on our local experience and field data from our field sites. The alternate hypothesis for this trial is that an infant of a lactating woman receiving BEP alone for 6 months or in combination with a single prophylactic dose of azithromycin at 42 days of age has a mean length velocity is greater than 0.12 cm/month that of an infant of a lactating woman not receiving an intervention at 6 months. The sample size takes multiple comparisons into account and is based on the primary outcome of length velocity with an effect size of difference of 0.12 cm per month between the arms (i.e., 0.72 cm difference at 6 months), a 1-sided test, power of 80% and an alpha of 0.025 to account for multiple comparisons (the lower alpha – Bonferroni correction was used). A drop-out rate of 14% (i.e., 10% loss to follow up and infant mortality rate of 4%) is assumed in the study, so the minimum total sample size required is 957 (319 lactating women in each arm).

7. Eligibility criteria

Inclusion Criteria

- a) Lactating women with a mid-upper-arm-circumference (MUAC) of < 23.0 cm
- b) Infants with a live birth outcome, captured within 168 hours (0-6 days)
- c) Individuals with the intention to stay in the catchment area for entire duration of trial after enrollment
- d) Individuals with the intention to exclusively breastfeed child for at least 6 months of age
- e) Individuals who have provided voluntary written informed consent

Exclusion Criteria

- a) Newborns with a birth weight of less than 1500 grams
- b) Newborns with a known congenital anomaly or other severe illness based on the study physician's assessment before enrollment.
- c) Lactating women with known allergies to peanut, lentils, chickpea or dairy products
- d) Individuals who were previously enrolled in the trial

8. Blinding

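### The LAZ, WLZ and WAZ nulls of at most 0.5 do not match the planned zero-difference tests, and the LAZ bar exceeds the planning effect on a reasonable z scale; one growth-velocity unit and the WLZ null also need correcting

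*SAP*

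**What the plan says.** **Z-score hypotheses.** SAP 5 gives the LAZ alternative as "Mean difference in LAZ >0.5 to look at comparisons between multiple arms" and sets the null at 0.5 or less. WLZ and WAZ follow the same pattern with the same 0.5. Protocol 5 and Protocol 10 (hypotheses to be tested) carry the same thresholds. Under the WLZ heading, all three places put the alternative on WLZ and the null on WAZ.

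**Role of the hypotheses.** Protocol 10 (general approach, item 2) says the secondary outcomes are analysed by predefined hypothesis and that conclusions rest on formal testing.

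**Planned analysis.** Protocol 10 (analysis approach) compares "weight velocity (gm/kg/day), LAZ, WLZ, and WAZ between the two intervention arms and the control arm using ANOVA". SAP 12 specifies one-way ANOVA, Tukey's test, an adjusted GLM and a mixed model with 95% confidence intervals. Neither states a shift of 0.5.

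**Planning effect.** SAP 6 sizes the trial on "an effect size of difference of 0.12 cm per month between the arms (i.e., 0.72 cm difference at 6 months". It uses "a 1-sided test, power of 80% and an alpha of 0.025 to account for multiple comparisons".

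**Growth velocity.** The threshold is 0.4 g/kg/day in Protocol 5, 7.2 and 10 and in SAP 5. Protocol 10 (definition of key variables, ii) instead defines the variable from baseline "until the age of 6 month, calculated as gm/kg/month". SAP 10.2 and SAP Table 3 use gm/kg/day.

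**The concern.** A null of at most 0.5 and a null of zero are different tests. An ANOVA p-value answers the second, while the written hypothesis asks the first. The plan does not say which decides whether a secondary outcome is met, so the analyst would have to choose, possibly after seeing results.

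For LAZ the choice matters a great deal. LAZ at 6 months is computed from the same 6-month length that enters the primary outcome, so the 0.72 cm planning effect has an implied size in z units. If that size is well below 0.5, a supplement that works exactly as planned would almost never meet the LAZ hypothesis as written, although the trial has ample power to show a LAZ difference from zero. The interim rule (Protocol 10, SAP 15) also allows a benefit recommendation on length velocity and/or a secondary outcome, so the ambiguity could matter before the final analysis.

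The unit conflict and the WLZ null are simpler. One leaves a Protocol outcome on a scale that does not match its threshold. The other pairs a null and an alternative that concern different variables.

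**Working it through.** **Inputs**
- Planning difference 0.12 cm/month, or 0.72 cm at 6 months (SAP 6).
- SD of velocity 0.5 cm/month, one-sided alpha 0.025, 274 evaluable and 319 randomised per arm, power 0.801 (Protocol 11).
- LAZ SD 0.96 to 1.04, from the 6-month results of a cited trial (Protocol 1.2). These are the only LAZ SDs in the documents.
- Centimetres per LAZ unit at 6 months, S. **Not in the documents**; assumed 2.0 to 2.4 cm.
- Baseline length assumed balanced by randomisation. The primary outcome is a change from baseline, whereas LAZ reflects attained length.

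**1. Reproduce the sample size.** n = 2 × (1.960 + 0.842)² × 0.5² / 0.12² = 272.5, so 273 by the normal approximation. The noncentral t gives power 0.7993 at 273 and 0.8007 at 274, matching the stated 274 and 0.801. Then 274 / 0.86 = 318.6, so 319, and 3 × 319 = 957. The stated figures reproduce, and they do so against a null of zero.

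**2. Put the two targets on one scale.** They coincide only if S = 0.72 / 0.5 = 1.44 cm.

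| S (cm, assumed) | 0.72 cm in z | 0.5 z in cm | 0.5 z relative to 0.72 cm | 0.5 z in cm/month |
|---|---|---|---|---|
| 2.0 | 0.36 | 1.00 | 1.39 | 0.167 |
| 2.16 | 0.33 | 1.08 | 1.50 | 0.180 |
| 2.4 | 0.30 | 1.20 | 1.67 | 0.200 |

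Outside the assumed range, the ratio is 1.25 at S = 1.8 and 1.74 at S = 2.5.

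**3. Is 1.44 cm credible on the plan's own SD?** A velocity SD of 0.5 cm/month over 6 months is an SD of 3.0 cm for length gain. If newborn length varies no more than 6-month length and the two are not negatively correlated, the 6-month SD is at least 3.0 / √2 = 2.12 cm. Dividing by a LAZ SD of 1.04 or 0.96 gives S of at least 2.04 or 2.21 cm. This is indirect, but it supports the assumed range and argues against 1.44.

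**4. Chance of meeting each LAZ criterion if the true effect is 0.72 cm.** SE = SD × √(2/274) = 0.0820 (SD 0.96) to 0.0889 (SD 1.04). Each row is a single pairwise comparison.

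| Criterion | Formula | Lowest | Highest |
|---|---|---|---|
| Reject a difference of at most 0.5, one-sided 0.025 | Φ((d − 0.5)/SE − 1.96) | 0.0005% (d 0.30, SD 0.96) | 0.02% (d 0.36, SD 1.04) |
| Observed difference above 0.5 | Φ((d − 0.5)/SE) | 0.7% (d 0.30, SD 0.96) | 5.8% (d 0.36, SD 1.04) |
| Reject a zero difference, one-sided 0.025 | Φ(d/SE − 1.96) | 92% (d 0.30, SD 1.04) | 99% (d 0.36, SD 0.96) |

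With Tukey's test for three arms the 1.96 becomes 2.348 (the 5% studentized range point divided by √2). The last row is then about 85% to 98%, and the contrast is unchanged.

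**5. Comparison without the assumed S.** The primary target is 0.12 / 0.5 = 0.24 SD. The LAZ bar is 0.5 / 1.04 to 0.5 / 0.96 = 0.48 to 0.52 SD. The denominators differ, so this does not prove a conflict, but it points the same way.

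**6. Growth velocity.** 0.4 g/kg/day × 30.4 = 12.16 g/kg/month. Read on the Protocol's per-month definition, 0.4 would be 0.4 / 30.4 = 0.013 g/kg/day.

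**The case against.** The strongest reply is that nothing in the operative analysis uses 0.5. ANOVA, Tukey's test and the GLM test zero, and SAP Table 3 shows pairwise differences with p-values. On that view the hypotheses are loosely worded effect targets and the analysis is already sound. This stands in part: the remedy largely brings the hypotheses into line with what will be run. But Protocol 10 ties conclusions to formal testing of the stated hypotheses, so the mismatch cannot be dismissed as style.

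A second reply is that a secondary outcome may carry a higher relevance mark than the primary planning effect, and that no passage says 0.5 z was derived from 0.72 cm. That is fair. The defect is a missing justification and a conflict with the planned test, not a failed sum.

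A reader might infer that a full success on the primary outcome would have to be reported as a LAZ failure. The documents do not support that:
- The primary null is also a non-zero margin, at most 0.12 cm/month. Read literally, a true effect of 0.12 rejects it only 2.5% of the time. Rejection needs an observed difference of about 0.12 + 1.96 × 0.5 × √(2/274) = 0.204 cm/month, or 1.22 cm over 6 months. That is 0.51 to 0.61 z on the assumed scale, already above 0.5, though formal rejection of the LAZ null would need about 0.66 to 0.67.
- Read with zero nulls throughout, as in the sample size calculation, both outcomes are well powered.

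The sharp contradiction appears only if LAZ is read literally and the primary is not.

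On the smaller items, the WLZ heading and alternative make the intent clear, and only one Protocol definition has the wrong unit. Both remain errors in outcome specification.

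**Conclusion.** The concern holds in this form. The LAZ, WLZ and WAZ nulls of at most 0.5 contradict the analysis planned for them, and neither document justifies the value. The primary null of at most 0.12 has the same structural defect.

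For LAZ, 0.5 z corresponds to about 1.4 to 1.7 times the planning effect. This rests on 2.0 to 2.4 cm per z unit and balanced baseline length. The multiple cannot be read from the plan's figures alone, because neither document gives centimetres per z unit. What follows from the documents alone is that the two targets agree only at 1.44 cm per unit.

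A true effect equal to the planning target would almost never meet the LAZ hypothesis as written (about 0.02% or less), though it would usually be detected against zero. It is not certain to miss 0.5 on the point estimate, where the chance of exceeding it is 0.7% to 5.8%.

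The factor of 30.4 in growth velocity is a conflict within Protocol 10 only. A reader might take it as a fault in the SAP threshold, but the SAP defines, tests and tabulates the outcome per day. The WLZ null is misprinted in both documents.

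**What to change.** - In Protocol 5 and 10 and SAP 5, restate the LAZ, WLZ and WAZ nulls as zero difference between arms and report each difference with a confidence interval. Protocol 7.2 repeats the 0.5 thresholds and should be aligned.
- If a relevance mark for LAZ is kept, derive it from 0.72 cm using the WHO 2006 standard named in Protocol 10 and SAP 10.2, and show the conversion. Do not fix a value such as 0.33 without it. State that the mark guides interpretation and is not the tested null.
- Treat the primary null of at most 0.12 in the same revision, so that the primary and secondary outcomes follow one convention.
- In Protocol 10 (definition of key variables, ii), change the growth-velocity unit to gm/kg/day.
- Write the WLZ null on WLZ in Protocol 5, Protocol 10 and SAP 5.

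The cost is wording in two documents. No data collection, sample size or planned model changes. The revision should be dated before unblinded results are seen.

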10. STATISTICAL ANALYSIS

General approach to data analysis

1. For the main study outcomes length velocity of the infant will be analyzed by predefined hypothesis in multiple arms. However conclusions on this part of the study will be based on formal hypothesis testing.
2. For secondary objectives (weight velocity, length-for-age, weight-for-length, and weight-for-age Z scores) will be analyzed by predefined hypothesis in multiple arms. However conclusions on this part of the study will be based on formal hypothesis testing.

Hypotheses to be tested

Primary

- a) To assess the efficacy of a fortified, balanced energy-protein supplementation intake using a ready-to-use product to lactating women of Mid-upper-arm-circumference (MUAC) of less than 23.0 cm for initial 6 month of exclusive breastfeeding with or without single prophylaxis dose of Azithromycin to infants at day 42 of age, in improving length velocity as the primary outcome at 6 months of age as compared to the standard of care..

Hypothesis to be tested:

H_a = Mean difference in length velocity of $>0.12\text{cm/month}$ to look at comparisons between multiple arms

H_o = Mean difference in length velocity of $\leq 0.12\text{cm/month}$ to look at comparisons between multiple arms

Secondary objective

- a) To assess the efficacy of a fortified, balanced energy-protein supplementation intake using a ready-to-use product to lactating women of Mid-upper-arm-circumference (MUAC) of less than 23.0 cm for initial 6 month of exclusive breastfeeding with or without single prophylaxis dose of Azithromycin to infants at day 42 of age, on weight velocity, length-for-age, weight-for-length, and weight-for-age Z scores as secondary outcome at 6 months of age as compared to the standard of care.

Hypothesis to be tested:

- i. **Growth velocity at 6 months of infant's age**

H_a = Mean difference in growth velocity of $>0.4\text{ gram/kg/day}$ to look at comparisons between multiple arms

- H_o = Mean difference in growth velocity of ≤ 0.4 gram/kg/day to look at comparisons between multiple arms
- ii. **Length-for-Age Z-score (LAZ) at 6 months of infant's age**
 H_a = Mean difference in LAZ >0.5 to look at comparisons between multiple arms
 H_o = Mean difference in LAZ ≤ 0.5 to look at comparisons between multiple arms
 - iii. **Weight-for-Length Z-score (WLZ) at 6 months of infant's age**
 H_a = Mean difference in WLZ >0.5 to look at comparisons between multiple arms

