This is a community-based, open-label, multiarm randomized controlled trial that will include parallel group assignments with a 1:1:1 allocation ratio in low-income squatter settlements in urban Karachi, Pakistan. The women in the control group (control arm) will receive standard counseling only, whereas the lactating women in the first intervention group (intervention arm 1) will receive two sachets of balanced energy-protein (BEP) supplementation per day from enrollment until the infant reaches six months of age. The lactating women in the second intervention group (intervention arm 2) will receive the same BEP supplementation as those in intervention arm 1 while their babies will also receive a single stat dose (20 mg/kg orally) of Azithromycin at 42 days.

2. Objectives

The primary objective is to compare the efficacy of fortified, balanced energy-protein (BEP) supplements being consumed by lactating women for 6 months (intervention arm 1) with or without a single prophylactic dose of oral azithromycin to the infant at 42 days of age (intervention arm 2) with that of standard exclusive breastfeeding and nutritional counseling alone (control arm) in improving length velocity among infants at 6 months (outcome). The secondary outcome is to compare the impact of the interventions on weight (or growth) velocity, Z-scores, other anthropometry measures of infants, maternal weight changes, breast milk quality, gut microbiota, and key micronutrient levels in both the mother and infant.

3. Study setting and study population

The trial is being conducted in the peri-urban communities of Karachi, Pakistan. The study population includes only lactating women of reproductive ages who have recently delivered and their infants. Lactating women between 13 and 49 years of age and their newborns are the study population.

4. Primary hypothesis

Length velocity at 6 months of infant's age

H_a = Mean difference in length velocity of $>0.12\text{cm/month}$ to look at comparisons between multiple arms

H_o = Mean difference in length velocity of $\leq 0.12\text{cm/month}$ to look at comparisons between multiple arms

5. Secondary hypothesis

Growth velocity at 6 months of infant's age

H_a = Mean difference in growth velocity of $>0.4\text{ gram/kg/day}$ to look at comparisons between multiple arms

H_o = Mean difference in growth velocity of $\leq 0.4\text{ gram/kg/day}$ to look at comparisons between multiple arms

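### The primary null is set at a difference of 0.12 cm/month or less, yet 0.12 is also the difference the trial is powered to detect, and no analysis method or decision rule tests against it

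*SAP*

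**What the plan says.** Protocol sections 5 and 10 and SAP section 4 give the same pair of primary hypotheses: a null of 0.12 cm/month or less and an alternative of more than 0.12. Protocol section 7.1 also writes the more-than-0.12 threshold into the primary outcome. SAP section 6 repeats the pair in prose. The null is a difference that "is equal or less than 0.12 cm/month (primary outcome"). Under the alternative, an infant in an intervention arm "has a mean length velocity is greater than 0.12 cm/month that of an infant" in the control arm.

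SAP section 6 also uses 0.12 in another role. It says "we hypothesized the effect size to be 0.12 cm/month", and it bases the sample size on length velocity "with an effect size of difference of 0.12 cm per month between the arms", with a one-sided test, alpha 0.025 and 80% power. Protocol section 11 gives the same calculation, "based on the primary outcome of length velocity in LW trial with 1-sided testing": difference 0.12, SD 0.5, 274 per arm, 319 after 14% drop-out, actual power 0.801.

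The SAP objective (section 2) is a comparison "in improving length velocity among infants at 6 months (outcome"), with no minimum margin. Protocol section 10 says that "length velocity of the infant will be analyzed by predefined hypothesis in multiple arms" and that conclusions will rest on formal hypothesis tests. The methods named are ANOVA adjusted for birth weight and age at enrolment (protocol section 10), and one-way ANOVA with Tukey's test, an adjusted general linear model and a mixed or repeated-measures model with 95% confidence intervals (SAP section 12).

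The secondary hypotheses have the same form, with 0.4 g/kg/day and 0.5 Z in place of 0.12.

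**The concern.** A null of 0.12 or less means that a true difference of exactly 0.12 belongs to the null. A valid one-sided 0.025 test of that null rejects at most 2.5% of the time at that value, so 0.12 cannot also be the difference detected with 80% power.

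The analysis sections do not settle which role is meant. ANOVA, Tukey and the general linear model, as described, test for no difference, so a significant result would not establish the written alternative. A lower confidence limit could be compared with 0.12, but neither document says that it will be. The interim benefit rule gives no margin either.

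The success criterion for the primary endpoint is at stake. Protocol section 10 ties the conclusion to the predefined hypothesis. A literal reader and an analyst who runs the named tests could reach opposite conclusions from the same data, and the choice between them could be made after the results are known.

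**Working it through.** **Inputs.** Difference 0.12 cm/month, SD 0.5, alpha 0.025, 274 per arm, 14% drop-out, power 0.801 (protocol section 11); one-sided test, 80% power (SAP section 6); equal allocation (SAP section 9). True differences other than 0.12 and family-wise levels for Tukey are assumptions.

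**Step 1: reproduce the plan's figure.**
- SE = SD × √(2/n) = 0.5 × √(2/274) = 0.0427.
- Degrees of freedom = 2 × 274 − 2 = 546; one-sided 0.025 critical t = 1.964.
- With a null of zero and a true 0.12, noncentrality = 0.12/0.0427 = 2.809. Power is 0.7993 at 273 per arm and 0.8007 at 274, which matches the stated 274 and 0.801.
- 274/0.86 = 318.6, rounded up to 319; 3 × 319 = 957.

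Power depends only on the true difference minus the null value. A null of 0.12 with a true difference of 0.24 would give the same figures, but neither document assumes 0.24. With 0.12 as the true difference, as SAP section 6 says, the implied null is zero.

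**Step 2: power against the written null at 274 per arm.** Noncentrality = (true difference − 0.12)/0.0427.

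| True difference (cm/month) | Power, null of zero | Power, null of 0.12 or less |
|---|---|---|
| 0.12 | 80.1% | 2.5% |
| 0.15 | 93.9% | 10.4% |
| 0.18 | 98.8% | 28.8% |
| 0.20 | 99.7% | 46.4% |
| 0.24 | above 99.9% | 80.1% |

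**Step 3: what counts as success.**
- Zero null: observed difference above 1.964 × 0.0427 = 0.084.
- Written null: observed difference above 0.12 + 0.084 = 0.204.
- An observed difference of exactly 0.12 has a 95% CI of 0.12 ± 0.084, or 0.036 to 0.204. It excludes zero but does not establish more than 0.12.

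**Step 4: how often the two readings conflict.** This is the probability of rejecting the zero null but not the written null, that is, the difference between the two powers. At a true 0.12 it is 0.801 − 0.025 = 0.776. It varies with the true difference:

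| True difference | 0 | 0.06 | 0.12 | 0.20 | 0.24 |
|---|---|---|---|---|---|
| Probability of conflict | 2.5% | 29% | 78% | 53% | 20% |

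**Step 5: the same check with Tukey** (three groups, 3 × 274 − 3 = 819 error degrees of freedom, true 0.12).
- Assumed 5% family-wise level: critical t 2.348; lower limit 2.348 × 0.0427 = 0.100; conflict probability 0.65 to 0.67, depending on whether the upper limit is 0.204 or Tukey's 0.220.
- Assumed 10%: critical t 2.055; lower limit 0.088; conflict probability about 0.75.

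**Step 6: size needed if 0.12 really were a margin** (80% power, one-sided 0.025).

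| Assumed true difference | n per arm | n per arm ÷ 0.86, rounded up |
|---|---|---|
| 0.15 | 4,362 | 5,073 |
| 0.18 | 1,092 | 1,270 |
| 0.20 | 615 | 716 |
| 0.24 | 274 | 319 |

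If the true difference is exactly 0.12, no sample size gives more than 2.5%.

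**The case against.** The strongest reply is that the intention is plain. The sample size, the named tests, the objective and the interim rule all work with a null of zero, and the SAP calls 0.12 the hypothesized effect. On this view the design difference was copied into the hypothesis statements by mistake, and nobody would run a shifted test because none is described. This is probably what happened, and it means that the sample-size arithmetic and the choice of tests are not invalidated. It does not remove the need for correction: the 0.12 statement is written out as the hypothesis to be tested, repeated in prose, built into the primary outcome, and tied to the trial's conclusions.

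Three narrower points also stand.
- The 78% applies at a true 0.12 and only if someone applies the written threshold; Step 4 gives the range. It is also unadjusted, and covariate adjustment could reduce the standard error.
- The sample sizes in Step 6 matter only if a margin is intended. The cited field experience, where "the difference was 0.06 cm/month at 3 months of age between these women" and unsupplemented women, came from more severely malnourished mothers, another dose and three months, so it says little about what margin would be realistic.
- Restating the null does not give Tukey 80% power. At 274 per arm and a true 0.12, per-comparison power is about 68% at an assumed 5% family-wise level and 77% at 10%. That shortfall is already in the plan and is not caused by the fix, but the power statement should name the test it describes.

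**Conclusion.** The concern holds: the primary hypothesis is wrong as written. Both documents put the null boundary at the value used as the true difference for 80% power, and no named method or decision rule uses that boundary. The stated 274 per arm and 0.801 are correct for a zero null. Against the written null, the same design has 2.5% power at the hypothesized effect and reaches 80% only at about 0.24 cm/month.

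Observed differences between 0.084 and 0.204 would be read in opposite ways. These limits assume SD 0.5, 274 evaluable infants per arm and an unadjusted one-sided 0.025 comparison. The point must be fixed because it defines success on the primary endpoint. The 0.4 g/kg/day and 0.5 Z hypotheses have the same fault of form; their power was not assessed.

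**What to change.** In protocol sections 5, 7.1, 7.2 and 10 and SAP sections 4, 5 and 6:

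- Restate the null as no difference for each prespecified comparison. If the confirmatory test is the one-sided 0.025 per-comparison test behind the sample size, write a null of zero or less against an alternative of more than zero; this keeps the stated power. If Tukey is to be confirmatory, write a two-sided null of zero.
- Describe 0.12 cm/month only as the difference the trial is powered to detect, and treat 0.4 g/kg/day and 0.5 Z as reference differences in the same way.
- State in protocol section 11 and SAP section 6 that the 80% power refers to a per-comparison one-sided 0.025 test.
- Correct the misprint under the weight-for-length heading, where the null names the weight-for-age score.

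This costs wording in both documents and one sentence on power. The sample size and data collection stay as they are.

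If a 0.12 margin is really intended, withdraw the claim of 80% power at 0.12, justify a true difference above 0.12, recalculate the sample size, and specify the shifted test or the confidence limit to be compared with 0.12. The sample size then rises unless a true difference of about 0.24 is assumed.
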